9 SAMPLE SIZE CONSIDERATIONS

There have yet to be any studies examining BPU response to tamoxifen. Thus, this study is a pilot design that will aim to enroll 30 patients who complete pre- and post-tamoxifen MBI. A sample size of 30 will have 80% power to detect a means change of 1 BPU quantitative unit (e.g. overall mean of 4.5 pre low-dose tamoxifen intervention, and post tamoxifen mean of 3.5), assuming a standard deviation of differences of 1.89 (effect size = 0.53), using a paired t-test with an α =0.05 two-sided significance level.

Allowing for potential study withdrawals, we will allow for a total of 50 patients to begin the low-dose tamoxifen intervention. In addition, women who are invited to participate may not have persistent BPU on their MBI performed at Study Visit 1. Prior pilot data showed that approximately half of women with prior high BPU had persistent high BPU on a current MBI. Therefore, up to 100 women will be screened with MBI to assess potential enrollment in the low-dose tamoxifen intervention. We will aim to balance enrollment of premenopausal and postmenopausal subjects.

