2 STUDY OBJECTIVE

To assess changes in background parenchymal uptake (BPU) on MBI before and after low-dose tamoxifen intervention (5 mg per day for 30 days or 10 mg per day for 30 days), among women with a history of high BPU. It is hypothesized that both subjective categorical and quantitative measures of BPU will decline with low-dose tamoxifen intervention.

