5.6 Low-dose tamoxifen intervention

Subjects will be enrolled to one of two arms of the study. The study arms will be identical, except for the dose of tamoxifen. For Arm 1, the dose of tamoxifen will be 5 mg per day for 30 days. For Arm 2, the dose of tamoxifen will be 10 mg per day for 30 days.

Participants will receive a prescription for tamoxifen. A physician co-principal investigator will order participant prescriptions, which will be filled through the Mayo Clinic Outpatient Research Pharmacy. For subjects in Arm 1, the research pharmacy will perform splitting of the standard tamoxifen tablets (available in either 10 mg or 20 mg doses) and over-encapsulation to arrive at 5 mg tablets.

Participant instructions for the tamoxifen medication will be as follows:

- Take one capsule per day for 30 days
- Take each dose at approximately the same time each day
- Capsules should be taken with water or a non-alcoholic beverage. Capsules can be taken with or without food.
- If you miss a dose, take the missed dose as soon as you remember it. However, if it is almost time for the next dose, skip the missed dose and continue your regular dosing schedule. Do not take a double dose to make up for a missed one.

Participants will also be given a "Drug Diary" log and asked to make notes of when each dose is taken and to record any symptoms experienced. Participants will be asked to return

Drug Diary logs and pill bottles at the Study Visit 2. Any remaining pills will be returned to the Outpatient Research Pharmacy for disposal.

Participants will be advised that they may elect to stop the tamoxifen medication at any time, should they experience unwanted side effects. Patients will be asked to contact study staff if they do choose to stop. Patients who start tamoxifen but choose to stop earlier than 30 days will be asked to return for their post-tamoxifen MBI test (Study Visit 2) at that time.

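### Does the 80% power in Section 9 fail because the 30 completers are divided between two tamoxifen doses?

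*Combined protocol and SAP*

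**What the plan says.** Section 9 calls the study a pilot and sets one target: "this study is a pilot design that will aim to enroll 30 patients who complete pre- and post-tamoxifen MBI". The power statement is "A sample size of 30 will have 80% power to detect a means change of 1 BPU quantitative unit". It is illustrated by a single pair of values, "overall mean of 4.5 pre low-dose tamoxifen intervention, and post tamoxifen mean of 3.5", and rests on a paired t-test with an SD of differences of 1.89 at a two-sided 0.05 level. To cover withdrawals, "we will allow for a total of 50 patients to begin the low-dose tamoxifen intervention".

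Section 5.6 introduces the doses: "Subjects will be enrolled to one of two arms of the study", with 5 mg per day in Arm 1 and 10 mg per day in Arm 2. Section 2 frames the objective as the change in BPU "before and after low-dose tamoxifen intervention (5 mg per day for 30 days or 10 mg per day for 30 days", and its hypothesis is a decline with low-dose tamoxifen. It states no separate hypothesis for each dose and no comparison of doses. The only balance that Section 9 mentions concerns menopausal status: "We will aim to balance enrollment of premenopausal and postmenopausal subjects".

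**The concern.** The power calculation does not mention the arms, and the section that defines the arms does not mention power. No section gives an allocation ratio or a planned number per dose, or uses a word such as pooled or combined for the analysis. There is no analysis section beyond Section 9 to settle it.

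A reader who sees two arms and one power figure could take the 80% to apply to each dose. If results were then tested dose by dose, an arm of about 15 women would miss a real 1-unit decline roughly half the time. A non-significant result could be misread as showing that the dose does not lower BPU. In a pilot meant to inform later work, that could count unfairly against a dose. The unstated split also affects the pooled test in principle: if the doses differ in effect, the split determines the average change being tested.

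**Working it through.** **Inputs.** From Section 9: 30 completers, mean change 1 unit, SD of differences 1.89, paired t-test, two-sided α = 0.05, at most 50 starters. From Section 5.6: two arms. The number per arm is not in the documents; an equal split is an assumption, and other splits are shown.

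**Formula.** Power = P(|T| > t(0.975, n−1)), where T is noncentral t with n−1 degrees of freedom and noncentrality (change/SD) × √n.

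**Step 1: the stated figure.** Effect size = 1/1.89 = 0.529, which rounds to the stated 0.53. With n = 30, noncentrality = 0.529 × √30 = 2.898 and the critical value is 2.045. Power = 79.98%. The stated 80% reproduces.

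**Step 2: by-dose power, if such a test were run.** Same change, SD and α:

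| Completers in one arm | Power for 1 unit |
|---|---|
| 10 (of a 10/20 split) | 32% |
| 15 (equal split of 30) | 48% |
| 20 (of a 10/20 split) | 61% |
| 25 (all 50 complete, equal split) | 72% |

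At n = 15, the change detectable with 80% power is 1.47 units, and the 95% CI half-width is 2.145 × 1.89/√15 = 1.05 units. At n = 25 these are 1.10 and 0.78 units.

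**Step 3: could the 80% be meant for each arm?** That needs 2 × 30 = 60 completers, and at most 50 women may start. So 80% in both arms is excluded by Section 9's own cap. One arm alone could reach 30, for example in a 30/20 split of 50.

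**Step 4: which test does the text describe?** Section 9 gives the measure (quantitative BPU), the test, the sample size, α, the sidedness and one overall pair of means. It sets 30 as the target for the study and 50 as a total starting the low-dose intervention. Section 2 defines that intervention as either dose. Together these describe one before-after test over all completers.

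**Step 5: does having two doses damage the pooled test?** Take assumed true changes of 0.5 and 1.0 with 15 women per dose. The average is 0.75, and simulated pooled power is 55%. A single group of 30 with a change of 0.75 has noncentrality (0.75/1.89) × √30 = 2.174 and power 56%. Nearly all of the loss comes from assuming a smaller average effect, and almost none from having two arms. With changes of 0.5 and 1.5 (average 1.0), pooled power is 78% if 1.89 is the SD within each arm. If 1.89 is the SD over all women, the within-arm SD is √(1.89² − 0.5²) = 1.82, and simulated power is about 81%.

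**The case for a change.** The strongest case for a change is that the protocol itself created two dose arms, so by-dose results are a foreseeable output, and the plan gives no warning of how imprecise they will be. The word overall appears only inside an example and does not name a primary test. Section 2 lists categorical and quantitative BPU without ranking them. If the doses differ in effect, the split matters: with assumed changes of 0.5 and 1.5, simulated pooled power is 62% when 20 of the 30 take the dose with the smaller effect and 89% when 10 do. A few sentences would remove the ambiguity at no cost in patients or visits.

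Part of this stands. The protocol does not say in words that the doses are pooled, gives no number per dose, and could not deliver 80% power in both arms. Anyone reporting results by dose should present them as estimates with confidence intervals.

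The rest carries less weight. The 62% and 89% depend on dose effects and an uneven split that appear nowhere in the documents. The misreading of a small arm is hypothetical, since no section plans to test or compare doses. Low power for an unplanned analysis is not a fault in the calculation for the planned one.

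**Conclusion.** The concern does not call for a change. The stated power is right to within rounding (79.98% against 80%) for the one test that Section 9 describes, and Sections 2 and 9 read together point to that test. The total of 50 starters excludes the only reading under which the figure would be wrong for both arms. The 48% is correct arithmetic, but it applies to a by-dose test that the protocol does not propose, under an equal split that it does not state.

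What remains is missing descriptive detail: pooling is implied but not spelled out, and the number per dose is not given. Analysts would reasonably fill this by running the paired test over all completers and describing each dose with its mean change and interval (half-width about 1.05 units with 15 women). Writing it down would not alter the design, the sample size or the conclusion from the planned test.

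This rests on Section 9's own assumptions, an average change of 1 unit and an SD of differences of 1.89, and on no confirmatory claim being made for a single dose.

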10 CONFLICT OF INTEREST

Mayo Foundation and two of the co-investigators ([name], [name]) on this protocol have a conflict of interest, due to licensing arrangements between Mayo Foundation and the manufacturer of the CZT detectors, Gamma Medica – Ideas, for rights to the hardware and software technology developed for low dose MBI. This conflict is noted in all the consent forms. Neither [name] nor [name] will be permitted to consent subjects for the study. None of the other investigators have a conflict of interest.

